#### Fumaric acid esters safety:

Very common adverse reactions include flushing, diarrhoea, and mild forms of lymphocytopenia and leukocytopenia.

Common adverse reactions include gastrointestinal disorders (bloating, cramps, and flatulence), severe forms of lymphocytopenia, and transient eosinophilia.

Trial treatment discontinuation criteria specific to subjects in the fumaric acid esters group, are provided in Section 10.8.2.

For further details, see the SmPC for Fumaderm®.

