### 10.8.2 Specific to subjects allocated to fumaric acid esters

Progressive multifocal leukoencephalopathy (PML) cases have occurred with fumaric acid esters and other products containing fumarates in the setting of moderate to severe prolonged

lymphopenia. PML is an opportunistic infection caused by John-Cunningham virus, which may be fatal or result in severe disability. Hence:

- If the lymphocyte count drops below  $0.7 \times 10^9/L$ , the dose should be halved. If during a follow-up check **after 4 weeks** the lymphocyte count remains below this value, then treatment with fumaric acid esters must be discontinued.
- If the lymphocyte count drops below  $0.5 \times 10^9/L$ , treatment with fumaric acid esters must be discontinued.
- If the leukocyte cell count drops below  $3 \times 10^9/L$ , treatment with fumaric acid esters must be discontinued immediately.
- Subjects should be discontinued from treatment with fumaric acid esters if any of the following applies:
  - a) Blood creatinine levels  $> ULN$ .
  - b) Clinically significant changes in haematology values or confirmed proteinuria or haematuria not related to an ongoing urinary tract infection or renal calculus/nephrolith (at the discretion of the investigator).

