### **13.3.8.4 Clinical laboratory evaluation**

The change in each of the laboratory parameters from baseline to Week 24 will be summarised as mean, SD, median, minimum and maximum values for each treatment group.

Laboratory parameters will be classified as 'low', 'normal' or 'high', depending on whether the value is below, within or above the reference range, respectively. A shift table will be produced showing the categories at baseline against those at Week 24. Subjects with laboratory parameters outside the reference range will be listed.

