### **13.3.10 General principles**

All statistical analyses of efficacy endpoints will be based on the FAS and safety endpoints on the safety analysis set (SAS). All significance tests will be two-sided using the 5% significance level. All CIs will be presented with 95% degree of confidence. No corrections for multiplicity will be performed.

If not mentioned otherwise, endpoints will be summarised descriptively at each visit by treatment and in total.

An observed-cases approach will be used for tabulations of data by visit (i.e. involving only those subjects who attended each specific visit). For categorical endpoints number of subjects not attending each specific visit will also be added.

Categorical data will be summarised using the number and percentage of subjects in each category. Continuous data will be summarised using the mean, median, SD, minimum, and maximum values.

In general, for endpoints evaluated as change from baseline and/or where a baseline adjustment is applied, baseline is defined as information collected at the randomisation visit (Visit 2), if not otherwise stated. If the assessment is not available at the randomisation visit but at the screening visit (Visit 1) then this will be used instead.

All the analyses specified in the protocol will be reviewed in relation to the blinded data obtained and the statistical analysis plan update will be finalised before breaking the randomisation code.

Any changes from the statistical analysis planned in this clinical trial protocol will be described and justified in the statistical analysis plan update (SAPU) and/or in the clinical trial report dependent on the type of deviation.

For endpoints evaluated over time, plots will be made to explore the trajectory with time.

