### *Reduced absolute neutrophil count*

During the 12-week placebo-controlled clinical trial period in patients with psoriasis, a decrease in absolute neutrophil count (ANC) was observed in 5.6% of patients receiving Kyntheum®, which was generally transient and reversible. Grade 3 and 4 have been observed occasionally. None of the Grade 3 or 4 ANC decreases in the psoriasis subset overall were associated with a serious infection.

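### By-arm laboratory tables cover only baseline against Week 24, so earlier, transient or pre-stopping abnormalities reach a by-arm table only if reported as adverse events

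*Combined protocol and SAP*

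**What the plan says.** Section 13.3.8.4 gives three laboratory outputs:

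- a continuous summary by treatment group: "The change in each of the laboratory parameters from baseline to Week 24 will be summarised as mean, SD, median, minimum and maximum values";
- a low/normal/high classification: "A shift table will be produced showing the categories at baseline against those at Week 24";
- a listing: "Subjects with laboratory parameters outside the reference range will be listed".

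Section 13.3.10 sets the default for visit-based tables: "An observed-cases approach will be used for tabulations of data by visit (i.e. involving only those subjects who attended each specific visit". It also provides a general by-visit summary: "If not mentioned otherwise, endpoints will be summarised descriptively at each visit by treatment and in total".

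Section 10.8.2 sets laboratory rules for the fumaric acid esters arm only. They cover lymphocytes, leukocytes, creatinine, other haematology changes and urine findings, and lead to dose reduction or stopping. For low leukocytes, "treatment with fumaric acid esters must be discontinued immediately". Section 10.8.1 adds liver-enzyme rules for both arms.

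Under 9.5.2, a subject who stops treatment attends an early termination visit with the Week 24 assessments, then a follow-up visit timed from it.

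**The concern.** The documents describe laboratory effects that a single late time point is poorly placed to show. Section 6.2.2 lists mild lymphocytopenia and leukocytopenia as very common on fumaric acid esters, and among the common reactions "severe forms of lymphocytopenia, and transient eosinophilia". Appendix 6 reports a fall in neutrophil count in 5.6% of brodalumab patients over 12 weeks, "which was generally transient and reversible".

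Loss from the Week 24 column is also not random with respect to the values being tabulated. Most of the laboratory stopping rules apply to one arm, so subjects with the most abnormal comparator values are among those least likely to have a Week 24 result. A subject whose dose was reduced and whose count recovered shows as normal. At stake is the between-arm description of measured values, which supports the objective of evaluating safety and tolerability of one drug against the other.

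**Working it through.** **1. Does another part of the plan supply by-arm results at other times?** The by-visit default in 13.3.10 applies to endpoints, and only where nothing else is specified. Laboratory parameters are not in the endpoint list in 13.3.4, and 13.3.8.4 does specify something else. The listing in 13.3.8.4 is not confined to Week 24, but it gives no count or percentage by arm. No worst-value or threshold table is planned.

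**2. Are early termination samples part of Week 24?**

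- For inclusion: 9.5.2 makes the assessments the same as at Week 24, and footnote 5 of Panel 2 treats the end-of-treatment date as captured at Week 24 or at early withdrawal.
- Against inclusion: 9.5.2 records early termination in the eCRF as an unscheduled visit, and 13.3.10 limits by-visit tables to attenders.

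No sentence settles it. The assignment is unspecified.

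**3. Checking the dropout inputs.** Section 13.1 assumes 50% dropout on fumaric acid esters and less than 40% on brodalumab. These reproduce its total response rates:

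- fumaric acid esters: 50% × (1 − 0.50) = 25%;
- brodalumab: 80% × (1 − 0.40) = 48%.

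The 40% limit is therefore the figure used for planning.

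**4. Coverage of the Week 24 column if early termination samples are not mapped to it.** Subjects per arm = 102 × (1 − dropout), assuming all randomised subjects are treated and dropouts have no Week 24 sample.

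| Dropout, fumaric acid esters / brodalumab | Fumaric acid esters present | Brodalumab present | Absent of 204 |
|---|---|---|---|
| 50% / 40% (13.1) | 51 | 61.2 | 51 + 40.8 = 91.8 (45%) |
| 30% / 10% (assumption) | 71.4 | 91.8 | 30.6 + 10.2 = 40.8 (20%) |
| 20% / 5% (assumption) | 81.6 | 96.9 | 20.4 + 5.1 = 25.5 (12.5%) |

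Because 13.1 says less than 40% for brodalumab, 45% is an upper figure on the planning assumptions.

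**5. One documented transient effect.** Applying the 5.6% to this trial gives 0.056 × 102 = 5.7, about 6 brodalumab subjects with a fall in neutrophil count. If all recover by Week 24, the Week 24 table shows none. If all persist and dropout is unrelated, it shows 5.7 × 0.60 = 3.4, about 3.

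**6. Are there other samples to use?** Section 11.6.1.2 gives about 60 mL in total at 6 to 12 mL per visit: 60/12 = 5 draws to 60/6 = 10 draws. Assuming one draw each at screening, baseline and Week 24, that leaves 2 to 7 others. The laboratory rows of Panel 2 were not available for this check, so the number is inferred. The 4-week lymphocyte recheck in 10.8.2 also implies on-treatment sampling.

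**The case against.** The strongest answer is that the safety objective does not rest on the laboratory tables. Panel 3 gives its endpoint as the frequency of AEs and SAEs by preferred term. Under 11.6.1.1 and Appendix 2, a clinically significant abnormality after screening must be reported as an AE. Appendix 2 also counts as AEs the reasons for unfavourable, unplanned changes of drug or dose. Section 13.3.8.1 tabulates treatment-emergent AEs by arm with percentages and rates, whether or not the subject reaches Week 24. The lymphocyte, leukocyte and creatinine rules in 10.8.2 are numeric, so a value that forces action should be recorded whatever the investigator's view of its significance.

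This stands. A reader might infer that abnormalities forcing a stop are absent from every between-arm safety table; the documents do not support that. A reader might also infer that the plan excludes early termination samples from Week 24; it is silent.

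The AE route still leaves a gap:

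- Abnormalities without a treatment consequence depend on the judgement of an investigator who is unblinded (8.3, 10.3.2), whereas the samples are analysed centrally.
- Action taken with the drug is recorded (12.2.1), but 13.3.8.1 plans no table by action. Its discontinuation summary concerns leaving the trial, so stopping the drug alone may not be counted there.
- Cytopenias are not among the AEs of special interest in 12.3.2.
- No table counts subjects by arm who cross the protocol's own laboratory limits.

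**Conclusion.** The by-arm display of measured laboratory values is limited to baseline and Week 24. Earlier, transient or pre-stopping abnormalities enter a by-arm table only through AE reporting. Because the rules in 10.8.2 act in one arm, the Week 24 column will tend to lose the most abnormal comparator values, and the measured-value comparison is open to that selection.

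On the plan's dropout assumptions, up to about 45% of subjects would be missing from the Week 24 column. At the lower assumed rates the figure is 12.5% to 20%. All three figures require that early termination samples are not mapped to Week 24. If they are mapped, fewer subjects are lost, but abnormalities that resolved before the last sample still do not show.

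It would be tempting to read 45% as a measure of hidden toxicity. It is not: the dropout figures are all-cause planning values, and the documents give no rate at which subjects would meet a laboratory stopping rule. The weakness is in a descriptive display and affects no hypothesis test, power or sample size. A statistical analysis plan update is foreseen in 13.3.10; it was not among the documents and may already address this.

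**What to change.** In 13.3.8.4, or in the statistical analysis plan update before the code is broken:

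- Add by-arm shift tables of baseline against the worst post-baseline on-treatment value, including early termination and unscheduled samples. Worst means lowest for lymphocytes, leukocytes and neutrophils, and highest for AST, ALT, creatinine and eosinophils.
- Add the number and percentage of subjects in each arm who cross, at any time on treatment, the laboratory limits already written in 10.8.1 and 10.8.2. Apply the same limits to both arms for description only.
- State how early termination samples are assigned to visits.
- Keep the baseline-to-Week 24 tables as a secondary display, with the number of subjects contributing in each arm.

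The cost is wording and a few descriptive tables from data already collected. There is one drawback. Worst-value tables that include unscheduled samples can find more abnormalities in the arm that is sampled more often, which the follow-up checks in 10.8.2 could make the fumaric acid esters arm. Show the same counts on scheduled plus early termination samples only, so that the effect of extra sampling can be seen.

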### **13.3.9 Interim analysis**

No interim analyses are planned.

### **13.3.10 General principles**

All statistical analyses of efficacy endpoints will be based on the FAS and safety endpoints on the safety analysis set (SAS). All significance tests will be two-sided using the 5% significance level. All CIs will be presented with 95% degree of confidence. No corrections for multiplicity will be performed.

If not mentioned otherwise, endpoints will be summarised descriptively at each visit by treatment and in total.

An observed-cases approach will be used for tabulations of data by visit (i.e. involving only those subjects who attended each specific visit). For categorical endpoints number of subjects not attending each specific visit will also be added.

Categorical data will be summarised using the number and percentage of subjects in each category. Continuous data will be summarised using the mean, median, SD, minimum, and maximum values.

In general, for endpoints evaluated as change from baseline and/or where a baseline adjustment is applied, baseline is defined as information collected at the randomisation visit (Visit 2), if not otherwise stated. If the assessment is not available at the randomisation visit but at the screening visit (Visit 1) then this will be used instead.

All the analyses specified in the protocol will be reviewed in relation to the blinded data obtained and the statistical analysis plan update will be finalised before breaking the randomisation code.

Any changes from the statistical analysis planned in this clinical trial protocol will be described and justified in the statistical analysis plan update (SAPU) and/or in the clinical trial report dependent on the type of deviation.

For endpoints evaluated over time, plots will be made to explore the trajectory with time.

### **13.3.11 Handling of missing values**

Missing data for categorical endpoints will be imputed with non-responder imputation. Missing data for continuous endpoints will be dealt with by a mixed model for repeated measurements.

## Appendix 1 Abbreviated eligibility criteria in accordance with CDISC requirements

Inclusion criteria in accordance with CDISC requirements (see Section 9.2 and 9.3 for full eligibility criteria)		
#	Short definition	Detailed description
1	Signed and dated informed consent has been obtained.	
2	Men or women $\geq 18$ years of age at the time of screening.	
3	Subjects with chronic plaque type psoriasis	Chronic plaque type psoriasis means diagnosed for at least 6 months before randomisation
4	Subjects with moderate to severe plaque psoriasis in whom topical therapy only is not adequate and who are candidates for systemic therapy at randomisation	Defined at randomisation by: - PASI >10 and - Affected BSA >10% and - DLQI >10
5	Subject has no known history of active tuberculosis.	
6	Subject has a negative test for tuberculosis taken at screening (negative QuantiFERON test).	
7	A female subject of childbearing potential is eligible to participate if she is not pregnant. This must be confirmed by a negative serum beta hCG pregnancy test at screening.	Female subjects are considered of childbearing potential unless they have undergone hysterectomy, bilateral salpingectomy or bilateral oophorectomy, or have been post-menopausal for at least one year prior to first visit.
8	Female subjects of childbearing potential must be willing to use highly effective contraception at trial entry and until 15 weeks after end of treatment. For subjects randomised to fumaric acid esters: oral contraceptive pills must be used with an additional contraceptive method (e.g. condom by partner, diaphragm, contraceptive gel, vaginal ring, etc.)	Highly effective contraception is defined as follows: • Sexual abstinence (when this is in line with the preferred and usual life style of the subject) • Vasectomised partner (given that the subject is monogamous) • Bilateral tubal occlusion • An intrauterine device (IUD) • Intrauterine hormone-releasing system (IUS) • Combined (oestrogen and progestogen containing) hormonal contraception associated with inhibition of ovulation (oral, intravaginal, transdermal) • Progestogen-only hormonal contraception associated with inhibition of ovulation (oral, injectable, implantable)
9	Male subject with a female partner of childbearing potential who is willing to use adequate contraceptive methods. Male subjects should not donate sperm in this period.	Adequate contraceptive measures as required by local regulation or practice for at least 15 weeks following last dose of investigational product.
10	Subject and/or subject's designee is/are capable of administering subcutaneous injections.	

Exclusion criteria in accordance with CDISC requirements (see Section 9.2 and 9.3 for full eligibility criteria)		
#	Short Definition	Detailed description
1	Previous or current systemic treatment of plaque psoriasis or known contraindication for systemic therapy.	
2	Previous or current PUVA (psoralens and ultraviolet A) therapy.	
3	Washouts and non-permitted drugs:	
a) Have received phototherapy (UVA light therapy without psoralens, UVB light therapy, excimer laser, tanning beds etc.) within 4 weeks of baseline.
 
b) Have had topical psoriasis treatment within 2 weeks of baseline (exceptions: bland emollients without urea or beta or alpha hydroxy acids).
 
c) Have received any biologic immune modulating treatment used for indication other than psoriasis within 4 weeks of baseline or within a period of 5 half-lives of the received treatment, whichever is longer.
 
d) Have received any other systemic immune modulating treatment (including but not limited to oral retinoids, methotrexate, calcineurin inhibitors, oral or parenteral corticosteroids etc. used for indication other than psoriasis) within 4 weeks of baseline or within a period of 5 half-lives of the received treatment, whichever is longer.

4	Clinically important active infections or infestations, chronic, recurrent or latent infections, infestations or immunocompromised (e.g. HIV).	
5	Presence of significant uncontrolled cerebral, cardiovascular, respiratory, hepatic, renal, gastrointestinal, endocrine, haematologic, neurologic, or neuropsychiatric disorders.	
6	Clinically significant abnormal values at screening within assessments of biochemistry, urine, and haematology (such as differential blood count and platelets) at the discretion of the investigator.	

Exclusion criteria in accordance with CDISC requirements (see Section 9.2 and 9.3 for full eligibility criteria)		
#	Short Definition	Detailed description
7	Subjects with any of the following laboratory abnormalities at screening: 
 
a) Leukocyte cell count below <math>3 \times 10^9/L</math> or lymphocyte count below <math>0.7 \times 10^9/L</math>.
 
b) Aspartate aminotransferase (AST) or alanine transferase (ALT) <math>> 2 \times</math> ULN (upper level of normal limit).
 
c) Absolute neutrophil count <math>< 2 \times 10^9/L</math>.
 
d) Serum creatinine <math>> ULN</math>.
 
	
8	Subjects with severe gastrointestinal diseases including, but not limited to, ventricular and duodenal ulcers.	
9	Subject with a known history of Crohn's disease or history of psoriatic arthritis with a need for treatment.	
10	Planned surgery, which in the opinion of the investigator would influence the planned treatment of the IMP.	
11	History of depressive disorder within the last 2 years including current anti-depressive treatment.	
12	Any positive finding in history of suicidal behaviour based on the C-SSRS questionnaire at screening or baseline.	
13	Any positive finding in suicidal ideation of level 4 or 5 based on the C-SSRS questionnaire at screening or baseline.	
14	A PHQ-8 score of $\geq 10$ corresponding to moderate to severe depression at screening or baseline.	
15	History of cancer.	
 
a. Subjects who have had basal cell carcinoma, localised squamous cell carcinoma of the skin or in situ carcinoma of the cervix are eligible provided that the subject is in remission and curative therapy was completed at least 12 months prior to the date informed consent was obtained.
 
b. Subjects who have had other malignancies are eligible provided that the subject is in remission and curative therapy was completed at least 5 years prior to the date informed consent was obtained.
 

16	Known or suspected hypersensitivity to component(s) of the IMPs.	

TRIAL ID: LP0160-1327	DATE: 17-APR-2018	VERSION: 4.0 PAGE 83 OF 108
-----------------------	-------------------	--------------------------------

Exclusion criteria in accordance with CDISC requirements (see Section 9.2 and 9.3 for full eligibility criteria)		
#	Short Definition	Detailed description
17	Current or recent involvement in other interventional clinical trial.	Current participation in any other interventional clinical trial, ending another interventional clinical trial less than 4 weeks prior to screening visit, or receiving other investigational agents (based on interview of the subject).
18	Current or recent treatment with any non-marketed drug substance.	Subjects who have received treatment with any non-marketed drug substance (i.e. an agent which has not yet been made available for clinical use following registration) within the last 4 weeks prior to screening visit
19	Previously enrolled in this clinical trial.	
20	In the opinion of the (sub)investigator, the subject is unlikely to comply with the clinical trial protocol (e.g. due to alcoholism, drug addiction or psychotic state).	
21	Subjects being the member of or being in close affiliation with trial personnel, sponsor or CRO.	Subjects in close affiliation with the trial personnel (e.g. immediate family member or subordinate), subjects being a member of the clinical trial personnel, or being an employee of the sponsor or a CRO involved in the trial.
22	Subjects under guardianship, hospitalised in a public or private institution, for a reason other than the research, or subject deprived of freedom.	
23	Female subjects who are pregnant or breastfeeding.	
24	Subject has any concurrent medical condition that, in the opinion of the investigator, could cause this trial to be detrimental to the subject	

## Appendix 2: Definitions of adverse events and serious adverse events

### Adverse event definition

*An AE is defined as any untoward medical occurrence in a patient or clinical investigation subject administered a pharmaceutical product and which does not necessarily have a causal relationship with this treatment. An AE can therefore be any unfavourable and unintended sign (including an abnormal laboratory finding), symptom, or disease temporally associated with the use of a medicinal (investigational) product, whether or not related to the medicinal (investigational) product. (ICH Harmonized Tripartite Guideline for Good Clinical Practice, E6 (R1)).*

This definition includes:

- accidental injuries, events related to trial procedures, reasons for any unfavourable and unplanned change in medication (drug and/or dose), clinically significant worsening of pre-existing conditions, or reasons for admission to hospital or surgical procedures unless these were planned before enrolment. It also includes AEs commonly observed and AEs anticipated based on the pharmacological effect of the IMP. In addition, any laboratory abnormality assessed as clinically significant by the (sub)investigator must be recorded as an AE.

